### **11.1.1 Adverse Events of Special Interest**

Adverse events of special interest will include psychiatric events of interest (categorized as psychosis/mania, suicidal, aggression and other miscellaneous psychiatric events) listed in [Table 4](#). Adverse event terms of special interest will be searched across the TEAE data and summarized with the total exposure (in subject-days).

**Table 4: Psychiatric Events**

Category	Preferred Term/Verbatim term
Signs and/or symptoms of psychosis/mania	Hallucination ( any type, including visual, auditory, tactile, mixed, etc. ) Delusion ( any type including somatic, persecutory, grandeur, reference ) Schizophrenia ( any type ) Psychotic disorder Transient psychosis Acute psychosis Paranoia Childhood psychosis Schizophreniform disorder Schizoaffective disorder Catatonia Mania Hypomania
Suicidal ideation and behavior	Depression suicidal Gunshot wound Intentional self-injury Non-accidental overdose Overdose Self injurious behavior Self injurious ideation Self-mutilation Suicidal ideation Suicidal attempt Completed suicide
Aggression and violent behavior	Aggression Anger Hostility Homicidal ideation Sexual offense Murder Imprisonment
Miscellaneous psychiatric events (include events with serious outcome only)	Abnormal behavior Agitation Amnesia Confusional state Depressed mood Depression Disorientation Emotional disorder

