8.1.6 Abuse, Misuse, Overdose, and Medication Error

Abuse, misuse, overdose, or medication error (defined as follows) must be reported to the sponsor according to the SAE reporting procedure whether or not they result in an AE/SAE as described in Section 8.2. Note: The 24-hour reporting requirement for SAEs does not apply to reports of abuse, misuse, overdose, or medication errors unless these result in an SAE.

The following categories are not mutually exclusive; the event can meet more than 1 category.

- **Abuse** – Persistent or sporadic intentional intake of investigational product when used for a nonmedical purpose (eg, to alter one's state of consciousness or get high) in a manner that may be detrimental to the individual and/or society
- **Misuse** – Intentional use of investigational product other than as directed or indicated at any dose (Note: this includes a situation where the investigational product is not used as directed at the dose prescribed by the protocol)
- **Overdose** – Intentional or unintentional intake of a dose of investigational product higher than the protocol-prescribed dose
- **Medication Error** – An error made in prescribing, dispensing, administration, and/or use of an investigational product. For studies, medication errors are reportable to the sponsor only as defined as follows:
 - Cases of subjects missing doses of the investigational product are not considered reportable as medication errors.
 - Medication errors should be collected/reported for all products under investigation.
 - The administration and/or use of an expired investigational product should be considered as a reportable medication error.

All investigational product provided to pediatric subjects should be supervised by the parent/LAR/caregiver.

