## 11.5 Other Safety Variables

### 11.5.1 Columbia-Suicide Severity Rating Scale

The Pediatric/Cognitively Impaired Version of the C-SSRS will be used in the study. The C-SSRS ([Posner 2007](#)) is a semi-structured interview that captures the occurrence, severity, and frequency of suicide-related thoughts and behaviors during the assessment period. The interview includes definitions and suggested questions to solicit the type of information needed to determine if a suicide-related thought or behavior occurred.

The C-SSRS contains 2 required items pertaining to suicidal ideation, 4 required items pertaining to suicidal behavior, and 1 required item pertaining to non-suicidal self-injurious behavior. In situations where there is a positive response to the screening questions, there are 8 additional suicidal ideation items and 2 additional suicidal behavior items which are completed. There are also 2 items for suicide and suicide behavior present during the interview. Thus, there is a maximum of 19 items to be completed. Most items are rated on a dichotomous scale (yes or no) or 3- or 5-point Likert scale. In addition, the total number of attempts (including interrupted and aborted attempts) is recorded. In the event of a positive categorical response the interviewer can provide text or narrative that further describes the thought or behavior).

Two versions of the C-SSRS will be used in this study as follows:

- The Pediatric/Cognitively Impaired - Lifetime Recent-Clinical version will be administered at the screening visit.
- The Pediatric/Cognitively Impaired -Since Last Visit - Clinical version will be completed at all study visits after the screening visit.

The number and percentage of subjects with positive responses for each suicidal ideation item, intensity of ideation item, suicidal behavior item, actual attempts item will be presented for overall and at each time point. Descriptive statistics for number of attempts of suicidal behavior will also be summarized.

Listings of the C-SSRS data will be provided for subjects with a positive response for the safety set.

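### SAP Table 4 files unqualified Overdose under suicidal events, so a caregiver's accidental extra capsule, if recorded as a TEAE under that term, could be counted as suicidal

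*SAP*

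**What the plan says.** SAP 11.1.1 names psychiatric events of special interest in four groups and states the method: "Adverse event terms of special interest will be searched across the TEAE data and summarized with the total exposure" in subject-days. SAP Table 4 supplies the terms under a column headed "Preferred Term/Verbatim term", so a match on either field is enough.

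The suicidal group includes, in sequence, "Intentional self-injury Non-accidental overdose Overdose Self injurious behavior". Nothing attached to the group restricts it by intent, seriousness or outcome. Table 4 does carry a restriction elsewhere: the last group is headed "Miscellaneous psychiatric events (include events with serious outcome only").

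Protocol 8.1.6 defines overdose as "Intentional or unintentional intake of a dose of investigational product higher than the protocol-prescribed dose". It requires every such case to be reported to the sponsor, with or without a resulting adverse event. Medication error is a separate category there, and the section states that one event may fall into more than one category.

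Protocol 6.2.2 has the parent or legal representative dispense the doses taken outside the research center. SAP section 20 lists the affected outputs: Table 14.3.3.3 (psychiatric events of special interest, by sex, safety set) and Listing 16.2.7.6.

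**The concern.** Because Table 4 already has an entry for non-accidental overdose, the plain term mainly adds overdoses that were accidental or of unstated intent. In this trial the obvious source is a dosing error by an adult, which says nothing about suicidal thinking in the child.

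The label matters because Protocol 1.2 names suicidality among the psychiatric events associated with SHP465. In a sample of about two dozen preschool children, a single count in a row headed as suicidal would be noticed and quoted. A reader of the table alone could not tell it from a true event.

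**Working it through.** No figure in the plan depends on this term list, so there is nothing to reproduce. The check sets the passages side by side and then gives the scale.

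**Can the rule count an accident?**

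1. Definition: under Protocol 8.1.6 an unintentional extra capsule is an overdose in the protocol's own vocabulary.
2. Timing: the TEAE window in SAP 11.1 runs from the first dose to 3 days after the last, so an extra home dose falls inside it.
3. Entry as an AE: not settled. Protocol 8.1.6 separates the overdose report from any resulting AE, and Protocol 8.1 defines an AE as an untoward medical occurrence. A symptom-free extra capsule may or may not reach the AE dataset.
4. Term: not settled. No section says which preferred term a caregiver's error would receive. Because the column also admits verbatim terms, a site that writes the protocol's word can produce a match.
5. Screening: SAP 11.1.1 has no step that removes accidents. Protocol 7.2.2.11 asks the investigator to tell accidental injury from self-harm or a suicide attempt, but Table 4 does not use that judgment.

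So if steps 3 and 4 are met, the written rule counts the event as suicidal.

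**Is an extra dose foreseeable?**

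- Center doses: the rich subset has Day 1 of four weeks plus Day 7 of Week 4, which is 5; the sparse subset has 4.
- Home doses for 20 completers: 10 × (28 − 5) + 10 × (28 − 4) = 230 + 240 = 470 of 560, or 84%.
- Protocol 6.3.2 describes 9-count bottles, against 7 doses in a week.
- SAP 8.2 treats 80–120% as compliant and has a category above 120%. One extra capsule gives 29/28 = 104%, which counts as compliant. The same capsule could be unremarkable in the compliance data and suicidal in Table 14.3.3.3.

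**How large would one count look?**

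Planned enrollment is about 24, with 20 completers and at least 2 + 3 = 5 girls among them (SAP 2.5).

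| Base | One event |
|---|---|
| About 24 in the safety set | 1/24 = 4% |
| 20 completers | 1/20 = 5% |
| Girls, minimum 5 completers | 1/5 = 20% |
| Boys, 20 − 5 = 15 completers | 1/15 = 7% |
| Exposure, 24 × 28 = 672 subject-days | 1.5 per 1,000 subject-days |

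The documents give no rate of accidental double dosing. As an assumption, let p be the chance per child of a record that meets steps 3 and 4. The chance of at least one among 24 is 1 − (1 − p)^24: 21% at p = 1%, 38% at 2%, 71% at 5% and 92% at 10%. This shows only how the result depends on p; it is not a forecast.

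**The case against.** The strongest reply is that the search is deliberately broad. For a rare and serious outcome, including terms of unknown intent protects against missing a case. A separate listing of these events is planned and all AEs are listed, so in about 24 children any stray hit can be checked one by one. The table is descriptive and no decision rule depends on it. All of this stands and keeps the point small. It does not correct the row itself: a broad search is sound for finding candidates, but the plan goes from search to count with no look at intent.

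The reply is also right against several stronger readings that a reader might infer.

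- *That an accidental double dose will be tabulated as suicidal.* The documents support only that it could be, because steps 3 and 4 above are open.
- *That Table 14.3.3.3 would contradict the C-SSRS tables.* One counts AE terms and the other counts interview responses. No rule requires them to agree, and the C-SSRS outputs are unaffected.
- *That the self-injury entries are misfiled too,* since SAP 11.5.1 describes "1 required item pertaining to non-suicidal self-injurious behavior" as its own C-SSRS item. The entries, including "Self injurious ideation Self-mutilation Suicidal ideation Suicidal attempt Completed suicide", do not say the injury was non-suicidal, and several are plainly suicidal. Keeping terms of open intent is a defensible choice. Moving them unless the C-SSRS is positive at the same visit would lose sensitivity and require linking two data sources.
- *That an expected number of false events can be had by applying an error rate to the 470 home doses.* No rate is in the documents, and the product would be a ceiling, since it treats every extra dose as a matching TEAE.

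The gunshot-wound entry has no shown effect here and is not part of the point.

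**Conclusion.** The overdose entry is wrong as written, and the matter is minor. SAP Table 4 places overdose of any intent in the suicidal category, while the protocol's definition expressly covers accidents and an adult gives the home doses. The rule can therefore label a caregiver's error as a suicidal event.

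The size is one count in a descriptive table: 4% of about 24 children, or 20% of girls if there are only five and the child is a girl. This rests on two assumptions that the documents leave open: the extra dose is entered as a TEAE, and its preferred or verbatim term is Overdose. The percentages also assume that all planned subjects are dosed and, for girls, that the safety set holds no more than the minimum number of female completers. PK results, the sample size and the C-SSRS summaries are not touched.

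**What to change.** In SAP Table 4, replace the bare entry with a qualified one: count Overdose in the suicidal category only when the record shows it was intentional or when intent cannot be excluded. Report accidental overdose and medication errors on a separate line of Table 14.3.3.3, outside the suicidal category. Keeping cases of unknown intent in the category preserves the sensitivity of the search.

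Add a sentence to SAP 11.1.1 saying whether overdose reports without symptoms, made under Protocol 8.1.6, enter the AE dataset, and who reviews intent before database lock.

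The cost is a short SAP text change, one more row in a table shell and its derivation, and a look at any matched record, probably few at this sample size. Study conduct and the visit schedule do not change. Where the record is silent on intent, the event stays in the category, so the rule does not depend on new data collection.

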**Table 4: Psychiatric Events**

Category	Preferred Term/Verbatim term
	Emotional distress
	Feeling abnormal
	Memory impairment
	Mood altered
	Mood swings
	Personality change
	Thinking abnormal
	Anxiety
	Fearfulness
	Phobia
	Panic attack
	Sleep disturbance
	Tics
	Obsessive or compulsive behavior
	Trichotillomania

A separate listing will be provided for AEs of special interest.

Adverse events of particular interest include insomnia (including AEs with preferred terms of 'INSOMNIA', 'INITIAL INSOMNIA', 'MIDDLE INSOMNIA', and 'TERMINAL INSOMNIA'), weight decrease and decreased appetite.

For each of these 3 AEs, the following information will be presented:

- Number and percentage of subjects reporting the TEAE
- Number of TEAEs
- Summary of onset day of first TEAE: The onset day of first TEAE is calculated as (onset date of first TEAE – date of first dose) + 1 for subjects who experienced the TEAE
- Summary of duration of TEAE while on study drug: The duration of each event is the number of days from the onset of the TEAE, while on study drug SHP465 6.25 mg, until the earlier of the end date of the TEAE or the date of last dosing + 3 days (if the date of last dosing is missing, the date of last day on study will be used). TEAEs that either overlap in time, or are adjacent in time will be merged into one TEAE only for the purposes of calculating duration of event. If a subject has multiple TEAEs that are not overlapping or adjacent in time, the durations will be averaged for that subject. Summary statistics are then based on the averaged subject durations. The calculated duration only includes the duration of TEAEs.
- Number and percentage of mild, moderate and severe TEAEs: Overlapping TEAEs with different preferred terms are counted as multiple TEAEs.

- Summary of the number of TEAEs per subject: Overlapping TEAEs with different preferred terms are counted as multiple TEAEs.
- Number and percentage of TEAEs that:
  - Resolved while on study drug
  - Ongoing
  - Dose interrupted
  - Dose withdrawn (and other action categories related to dose)
  - TEAEs leading to discontinuation
  - Number of subjects who discontinued investigational product due to the event

Also, for each of these 3 AEs, the following information will be presented by week:

- Number of subjects in the study
- Number and percentage of subjects with the TEAE
- Number of TEAEs
- Number and percentage of subjects who discontinued due to the TEAE
- Number and percentage of mild, moderate and severe TEAEs. If a subject has more than one TEAE in the same week, then the worst severity is counted.

In addition, for each subject, all occurrences of each of these 3 AEs will be listed separately by subject, start date and stop date. The information presented will include: subject, sex, age, race, ethnicity, preferred term/reported term, start date, stop date, onset day, study visit, last dose date, duration/imputed duration of TEAE (days), SAE, severity, and effect on doing.

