8.1.1 Severity Categorization

The severity of AEs must be recorded during the course of the event including the start and stop dates for each change in severity. An event that changes in severity should be captured as a new event. Worsening of pretreatment events, after initiation of investigational product, must be recorded as new AEs (for example, if a subject experiences mild intermittent dyspepsia prior to dosing of investigational product, but the dyspepsia becomes severe and more frequent after the dose of investigational product has been administered, a new AE of severe dyspepsia [with the appropriate date of onset] is recorded in the source document).

The medical assessment of severity is determined by using the following definitions:

Mild: A type of AE that is usually transient and may require only minimal treatment or therapeutic intervention. The event does not generally interfere with usual activities of daily living.

Moderate: A type of AE that is usually alleviated with specific therapeutic intervention. The event interferes with usual activities of daily living, causing discomfort but poses no significant or permanent risk of harm to the research subject.

Severe: A type of AE that interrupts usual activities of daily living, or significantly affects clinical status, or may require intensive therapeutic intervention.

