## 17. CHANGES TO ANALYSES SPECIFIED IN PROTOCOL

The PK parameters  $AUC_{0-\infty}$  and  $V_z/F$  for *d*- and *l*-amphetamine have been omitted from the PK analysis, given that only steady-state PK concentrations will be available. These parameters are not appropriate for calculation and interpretation in multiple dosing scenarios. There are no other changes from the PK analysis methods stated in the protocol.

Protocol section 9.8 (Safety Analyses) states: Treatment-emergent AEs are defined as AEs that started or deteriorated on or after the date of the first dose of investigational product, and no later than 3 days following the **first** dose of investigational product. Since this is a multiple-dose study and the dose will be administered daily as a single dose for 28 days, the definition of TEAE in the protocol will exclude the AEs started or deteriorated on or after the fourth dose, which will not be appropriate for safety analysis. The following definition for TEAEs is used in the Statistical Analysis Plan: Treatment-emergent AEs are defined as AEs that started or deteriorated on or after the date of the first dose of investigational product, and no later than 3 days following the **last** dose of investigational product.

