### **18.7 Missing Date Information for Adverse Events**

For AEs, incomplete (i.e., partially missing) start dates will be imputed and will follow the same rules as in Section [18.6.1](#). Incomplete stop dates will not be imputed.

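### SAP 11.1.1 averages a child's separate episodes of insomnia, weight decrease or decreased appetite, which can report a shorter duration for a child with more affected days

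*SAP*

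**What the plan says.** SAP 11.1.1 gives insomnia, weight decrease and decreased appetite their own summaries (SAP 20: Tables 14.3.3.4.1, 14.3.3.5.1 and 14.3.3.6.1). One line in each is headed "Summary of duration of TEAE while on study drug". It is built in four steps:

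- Each event runs from onset "until the earlier of the end date of the TEAE or the date of last dosing + 3 days".
- For this calculation only, "TEAEs that either overlap in time, or are adjacent in time will be merged into one TEAE".
- Episodes that remain separate are then combined: "If a subject has multiple TEAEs that are not overlapping or adjacent in time, the durations will be averaged for that subject".
- The table describes these one-per-child means, not the individual episodes.

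The same section plans the number of TEAEs, TEAEs per subject, onset day of the first TEAE, the number and percentage of TEAEs resolved on study drug and ongoing, incidence by week, and a listing of every occurrence with its dates and duration. It plans no summary of total days affected per child and no censoring mark on an episode that was cut. SAP 18.7 adds: "Incomplete stop dates will not be imputed".

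**The concern.** A reader of a duration line for a tolerability event is likely to take it as how long children were affected. The averaged value does not measure that once a child has more than one separate episode. A further episode shorter than the child's current mean lowers the reported value while the number of affected days rises.

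The cut-off adds to this. An episode still running at last dose + 3 days enters at whatever length remained after its onset, with nothing beside the duration to show that it is a minimum. A late-starting unresolved episode is then one of the short values that pull a child's mean down.

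Safety and tolerability are part of the primary objective (SAP 3.1), and about 24 children are expected (SAP 2.5). Few may contribute to any one of these duration lines, so a single value of this kind could move the summary.

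**Working it through.** The documents give no figure for this summary, so there is none to reproduce. The rule can be applied directly.

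**Inputs.** SAP 17 notes that "the dose will be administered daily as a single dose for 28 days". With the last dose on Day 28, the cut-off is Day 28 + 3 = Day 31 (Day 30 to Day 32 with the ±1 day). The SAP gives no day-count convention for duration. I use end − start + 1 and check the alternative. The episode patterns below are my assumptions.

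**Formula.** With k separate episodes totalling T days after truncation and merging, the reported value is T/k. A child with one episode of S days is reported as S. The child with more affected days gets the shorter value when T > S and T/k < S, that is, when S < T < k × S.

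**Averaging.**

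- One 20-day episode: 20/1 = 20. With a separate 2-day episode added: (20 + 2)/2 = 11, with 22 days affected. Condition: 20 < 22 < 40, met.
- Three separate 5-day episodes: 15/3 = 5, against 10 for a child with one 10-day episode. Condition: 10 < 15 < 30, met.
- Two separate 12-day episodes: 24/2 = 12, against 10. Condition: 10 < 24 < 20, not met. The order is kept.
- Counting end − start instead: (19 + 1)/2 = 10 against 19, and (4 + 4 + 4)/3 = 4 against 9. Both reversals remain.

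**Cut-off.**

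- An event that never resolves scores 31 − 2 + 1 = 30 days if it starts on Day 2, and 31 − 25 + 1 = 7 days if it starts on Day 25.
- An episode on Days 1–20 plus one starting on Day 27 and still ongoing: (20 + 5)/2 = 12.5, against 20 for the first episode alone, although at least 25 days were affected. With the last dose on Day 27 or Day 29 the value is 12.0 or 13.0.
- A child with onset on Day 3 and last dose on Day 5 is cut at Day 8 and scores 8 − 3 + 1 = 6, however long the event lasts.

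**How often.** The documents cannot answer this. As an illustration only, I placed episodes at random in a 31-day window and kept the pairs in which the multi-episode child had more affected days than a single-episode child. The reported duration was shorter in about 30% of such pairs with two episodes (3,729 of 12,561) and about 48% with three (6,731 of 14,021). This shows that the reversal is neither automatic nor a curiosity. It does not predict this trial.

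**Can the other table lines recover T?** Not in general. Merging applies to duration only, so the TEAE counts use unmerged records. Protocol 8.1.1 says: "An event that changes in severity should be captured as a new event". A 20-day event recorded as 10 days mild and then 10 days moderate is merged to a duration of 20 but counts as 2 TEAEs. Count × duration gives 2 × 20 = 40, not 20.

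**The case against.** The case for leaving the SAP alone is substantial. The window is declared: the line is labelled as time on study drug, and its 3-day tail matches the TEAE definition in SAP 11.1. Merging comes first, so severity changes, which would normally be adjacent, are not averaged. For a child with one merged episode the line already gives days affected within the window. Nothing in the SAP ranks children, tests this summary or bases a decision on it. With about 24 children, total days can be worked out from Listings 16.2.7.7 to 16.2.7.9.

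All of that stands, and it makes this a minor point. It does not remove it: the tables omit total days, the counts beside the average cannot restore them, and working from the listing means doing by hand what the table could show.

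Two stronger readings are tempting, and the documents do not support them. A reader might infer that a child with more affected days is always reported with a shorter duration; the two 12-day episodes above show otherwise. A reader might also infer that the SAP treats unresolved events as finished. That is true only of the length entered in the duration statistic, because the same section counts ongoing and resolved events separately. What is missing is the link between those counts and the durations that were cut.

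**Conclusion.** The point holds as a possibility built into the rule, not as a certain distortion. The per-child duration is T/k with uncensored truncation at last dose + 3 days. It can report a shorter duration for a child with more affected days, as in 11 against 20 days when 22 against 20 were affected. Against a single S-day episode this requires S < T < k × S. Truncation alone only shortens a value and need not reverse an order.

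The size in this trial is unknown, because the documents do not say how often separate episodes are expected. The conclusion rests on the literal wording of SAP 11.1.1 and, for the numerical cut-offs, on a last dose near Day 28. The effect is confined to one descriptive line in three tables. The change is a cheap improvement, not a correction on which any result depends.

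**What to change.** In Tables 14.3.3.4.1, 14.3.3.5.1 and 14.3.3.6.1, in place of or beside the averaged duration:

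- Summarise total affected days per child: the union of all that child's episodes from first dose, each ending at the earlier of its end date or last dose + 3 days.
- Give the same total as a percentage of the window from first dose to last dose + 3 days. With the last dose on Day 28 the window is 31 days, so 20 and 22 affected days become 20/31 = 65% and 22/31 = 71%. The percentage matters for children who stop early: the 6 days in the Day 5 example are 6/8 = 75% of that child's window.
- State how many children's values include an episode cut off at last dose + 3 days.
- State the day-count convention for duration.

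Do not restrict episode length to resolved episodes. In a window of about 31 days that would drop the longest unresolved episodes and bias the length downwards.

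The dates are already collected, and T is already the numerator of the planned average. The cost is SAP wording, minor programming and one or two more descriptive lines per table.
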